Several risk factors for CPSP have been established [9;10;11]. A wide interindividual range characterizes the sensation of pain; multiple factors influence the perception of pain, such as genetic determinants, neurological diseases affecting the central or peripheral nervous system, inflammatory modulation of tissues, and the presence of inflammatory mediators, as well as the experience of pain [12;13;14;15; 16]. CPSP is widely associated with iatrogenic nerve lesions and chronicity is also linked to the remodeling of the central nervous system which determines central sensitization phenomena [17;18]. Furthermore, psychological factors such as depression, pain catastrophizing, mood, and stress could influence the perception of pain [19;20;21;22].

Although surgery is a determining factor in the onset of chronic pain, some patient characteristics also appear to be predictive of an increased risk of persistent pain: young age [23], female sex [24], preoperative pain [25], high levels of acute postoperative pain [25] and psychosocial factors [26;27]. The most significant limitations of current awareness in this field are the heterogeneity of study methodology, including assessment of pain timing, different definitions of pain, and the small sample size of most of the previous studies.

Identifying risk factors for CPSP before surgery could help identify high-risk patients using risk prediction models and allocate preventative strategies [28;10]. Identification of risk groups in the patient population is critical to providing individualized pain treatment [29] and may help reduce long-term opioid use.

The present study aims to identify the risk factors of CPSP three months after surgery and, to develop a valid risk index to detect high-risk patients that considers the multifactorial etiology of CPSP.

Aim

The main objective of this multicenter observational study is to estimate the occurrence of CPSP three months after any type of surgery and identify risk factors for the development of a multivariate clinical prediction model of CPSP at three months.

Methods

This is a multicenter, prospective, observational study on adult patients requiring any type of surgical procedure. This study is designed and will be reported according to the STrengthening the Reporting of OBservational studies in Epidemiology (STROBE) statement. Ethics Committee approval is mandatory to begin registration at all recruitment centers.

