- Surgical complications (Y/N)
- Infectious complications related to surgery (Y/N)
- Malignancy (Y/N)

Questionnaires:

• Douleur Neuropathique in 4 questions (DN-4)

Outcome variable

The outcome variable is the presence of CPSP assessed 3 months after surgery and defined as an average pain intensity of at least 3 points on the NRS scale (one-dimensional pain scale - from 0 to 10 points) in the last three days and pain localized to the surgical field (or in the lesion area) projected into the innervation territory of a nerve located in this area, or referred to a dermatome [30;31].

Development of the risk index

Separate prediction models will be developed using data derived from investigations conducted at the relevant time points.

(1) Primary version of the risk index, made up of items derived from a systematic bibliographic search (compilation of the item pool).

(2) In a second phase, the Authors will analyze the associations between each of these indices and the probability of CPSP 3 months after surgery (dichotomous variable), evaluated using logistic regression models.

(3) Items that were found to be significant in the bivariate analyses will then be analyzed multivariately (logistic regression models).

(4) In a fourth step, the Authors will safeguard the results of the multivariate analyses by calculating the area under the ROC curve of the model, and then, the cut-off score for a high risk of developing CPSP will be identified with an optimal compromise between sensitivity and specificity.

(5) Finally, the items that will generate significant predictive factors in the logistic regression analyses will be collected into an index. For each value of this index, the Authors will calculate the proportion of patients who reported CPSP at 3 months after surgery.

Statistical analysis of results

The study population will be described by summarizing the variables collected in each period of evaluation of the subject (preoperative, perioperative before surgery, perioperative after surgery, three months post-operatively after surgery). In particular, the discrete variables will be reported in terms of absolute and relative frequency, and the continuous variables will be summarized via mean and standard deviation or via median and interquartile range, based on the symmetry of each distribution.

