The study population will be stratified based on the presence/absence of CPSP three months after surgery, and a comparison will be made between the two groups. In detail, the Student's T test for independent samples will be used in the case of normally distributed variables (normality assessed using the Kolmogorov-Smirnov test), the non-parametric Wilcoxon-Mann-Whitney test in the case of non-normally distributed variables, the Pearson Chi-Square in case of discrete variables or Fisher's exact test if the expected frequency is low.

Univariate and multivariate logistic regression models will be used to study the association between the probability of CPSP three months after surgery (dependent variable) and the collected variables (independent variables). The results of each model will be reported in terms of model parameters and odds ratios and their 95% confidence intervals. For each logistic model, the discriminated ability will be evaluated via the C-statistic of the area under the ROC curve and calibration via the Hosmer-Lemeshow test. To identify significant (preoperative and intraoperative) predictors of CPRS three months after surgery, backward elimination will be used with the threshold of 0.05 as the level to remain in the model. The parameters of the multivariate logistic regression model resulting from this process will be used to assign a score to each predictor. Internal validation will be conducted using bootstrapping to correct for optimism.

Given the observational nature of the study, as well as the large sample size and multicenter nature, any variable reporting a high proportion of missing values (>25%) will be eliminated from the analyses. Subjects in which more than half of the variables are missing will be excluded from the analysis. Lower proportions will lead to the use of the statistical technique of multiple imputations of missing data, assuming that the missing data are random (independent of the missing value, but dependent on other variables). Based on the total proportion of missing data, if this is relatively low (less than 5%) the possibility of analyzing only those subjects with all available data may also be taken into consideration.

For all statistical analyses, the significance level is set at p < 0.05 and the tests used are two-tailed.

Power analysis

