The sample size of the development dataset must be large enough to develop a prediction model equation that is reliable when applied to new individuals in the target population.

The authors estimate that approximately 1500 patients are necessary to develop a logistic model for clinical prediction of CPSP (presence/absence) three months after surgery.

The estimate of the sample size was performed following the methodological recommendations of Riley [33] and hypothesizing two scenarios with a cumulative incidence of CPSP 3 months after the intervention of 10% and 50%. It was necessary to hypothesize two scenarios since the aggregate incidence of CPSP in the

target population is not known in the literature. The information is available only based on the type of surgery and the estimate varies between 10% and 50%.

Assuming an incidence of 50% and that the final predictive model can explain more than 15% of the variability with 15 candidate parameters (risk of overfitting), a sample size of 1124 subjects is estimated for the development of a logistic predictive model, corresponding to 37 subjects with CPSP per parameter.

Assuming an incidence of 10% and that the final predictive model can explain more than 15% of the variability with 15 parameters, a sample size of 1799 subjects is estimated for the development of a logistic predictive model, corresponding to 12 subjects with CPSP by parameter. The sample size is reduced to 1440 individuals for the development of a final predictive model with 12 parameters.

Given the uncertainty on the estimated incidence of CPSP three months after surgery, a sample size of, at least, 1500 individuals is therefore sufficient to meet the main objective of the study.

Expected number of centers to enroll

Authors estimate that, at least, 10 centers are needed to enroll the study population.

Schedule

The calendar will be organized into three-time windows:

• First phase - Authorization from the Local Ethics Committee of the participating Center, patient enrollment, and first evaluations: from the 1st to the 12th month from the date of project approval.

• Second phase - completion of follow-up and sending of complete clinical documentation from the registered Centers: from the 12th month to the 18th month from the date of project approval.

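### Multivariable odds ratios reported after a p < 0.05 screen and backward elimination exaggerate weak predictors, and their 95% intervals, taken as a set, fall short of 95% coverage

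*Combined protocol and SAP*

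**What the plan says.** The *Aim* is to estimate how often CPSP occurs and to "identify risk factors for the development of a multivariate clinical prediction model of CPSP at three months". Risk factors are therefore a stated output as well as an ingredient of the index.

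Two significance filters act on the one development dataset. Step 3 of *Development of the risk index* says: "Items that were found to be significant in the bivariate analyses will then be analyzed multivariately (logistic regression models". *Statistical analysis of results* adds that "backward elimination will be used with the threshold of 0.05 as the level to remain in the model". The level is fixed throughout: "For all statistical analyses, the significance level is set at p < 0.05 and the tests used are two-tailed".

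For the univariate and multivariate logistic models alike, the plan states: "The results of each model will be reported in terms of model parameters and odds ratios and their 95% confidence intervals". The selected coefficients then feed the index: "The parameters of the multivariate logistic regression model resulting from this process will be used to assign a score to each predictor".

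The one safeguard is a single sentence: "Internal validation will be conducted using bootstrapping to correct for optimism". It does not say whether the screen and the elimination are repeated in each resample, whether coefficients are shrunk, or whether intervals are adjusted. The odds ratios are not labelled exploratory.

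**The concern.** A variable reaches the final model because its estimate in this sample was far enough from zero to pass two tests. A standard interval ignores that. A weak true predictor is seen only in the samples where chance made it look strong. A null item is kept only when its interval happens to exclude 1, so the interval of a retained null item can hardly ever contain the truth.

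At stake is the published list of risk factors. Readers would take the stated intervals at face value and could not tell which odds ratios are trustworthy. Index points are affected where inflation differs between predictors, because weak items gain points relative to strong ones.

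**Working it through.** **1. The plan's own figures.** The sample sizes in *Power analysis* follow from the shrinkage criterion n = P / [(S − 1) ln(1 − R²/S)]. S = 0.9 is my assumption. R² is 0.15 times its maximum, which is 1 − [φ^φ (1 − φ)^(1 − φ)]² at incidence φ.
- φ = 50%: maximum 0.75, R² = 0.1125, P = 15 gives 1,124, as stated.
- φ = 10%: maximum 0.478, R² = 0.072 (rounded), P = 15 gives 1,799 and P = 12 gives 1,440, as stated.

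The criterion limits overfitting of a model with P parameters. It does not address intervals computed after selection.

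**2. Number of candidates.** Counting one parameter per yes/no item and one fewer than the number of categories otherwise, *Data collection* lists 15 preoperative parameters, 15 recorded before surgery and 7 after surgery: 15 + 15 = 30, and 30 + 7 = 37. Separate models per time point are planned, so 37 applies at most to the last.

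**3. One coefficient, one filter.** Take N = 1,500 and a binary predictor with 30% prevalence (assumed).
- SE ≈ 1/√[N φ(1 − φ) × 0.3 × 0.7]. At 10% incidence this is 1/√28.35 = 0.188; at 50%, 1/√78.75 = 0.113.
- Let μ = ln(OR)/SE, and report the estimate only if |Z| > 1.96, with Z normal around μ. The chance of retention is P = Φ(μ − 1.96) + Φ(−μ − 1.96).
- The mean reported log OR relative to the truth is E(Z given |Z| > 1.96)/μ. Coverage is the probability that |Z − μ| < 1.96 given |Z| > 1.96.

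| True OR | Incidence | Log OR inflated by a factor of | Coverage if retained |
|---|---|---|---|
| 1.2 | 10% | 2.5 | 84% |
| 1.3 | 10% | 1.85 | 91% |
| 1.5 | 10% | 1.31 | 96% |
| 2.0 | 10% | 1.03 | 97% |
| 1.2 | 50% | 1.63 | 93% |
| 1.5 | 50% | 1.03 | 97% |

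At 10% incidence an OR of 1.2 is retained 16% of the time. A retained null item has coverage 0% and a mean apparent OR of about 1.55 (or its inverse).

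**4. The whole sequence.** Simulated studies of 1,500 patients went through the univariable screen, backward elimination at 0.05 and ordinary Wald intervals, with explained variability of about 15% (0.10 to 0.18 in the 15-or-30-candidate row).

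| Setting | Coverage after selection | Coverage, full model |
|---|---|---|
| 15 candidates (8 true), correlation 0 or 0.2; 10, 20, 50% incidence | 90.4–92.8% | not run |
| 27 candidates (16 true), correlation 0; 10%, 50% | 89.9%, 91.0% | 94.5%, 94.6% |
| 27 candidates (16 true), correlation 0.2; 10%, 50% | 78.5%, 83.5% | 94.5%, 94.5% |
| 15 or 30 candidates, correlation 0 or 0.2; 10%, 50% | 80–92% | 94–95% |
| 37 candidates (12 true), correlation 0 | 85–88% | not run |
| 37 candidates; 10%, 20% | 87.6%, 89.8% | 94.5–94.8% |

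**5. Where the shortfall comes from.** Retained null items count as misses. In the 27-candidate runs without correlation they were 4.6% and 4.1% of retained items (10%, 50% incidence). Leaving them out gives 89.9/(1 − 0.046) = 94.2% and 91.0/(1 − 0.041) = 94.9%, so they explain nearly all of the loss. At correlation 0.2 they were 7.4% and 6.5%, and leaving them out gives 78.5/0.926 = 84.8% and 83.5/0.935 = 89.3%. The remaining loss falls on true predictors, partly because correlated true predictors were dropped. In the other runs that separated them, true predictors kept 90 to 96%.

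**6. Inflation.** The mean inflation of retained true log ORs was 5–24% with 15 candidates, 14–22% with 37, and 8–59% in the 15-or-30-candidate runs. It is uneven. With 27 candidates, correlation 0.2 and 10% incidence, a true OR of 1.14 was reported as about 1.61 (coverage 70%), 1.28 as 1.67 (81%), 1.48 as 1.75 (90%) and 1.79 as 1.99 (92%). The ratio of log ORs between strongest and weakest fell from ln 1.794/ln 1.145 = 4.3 to ln 1.99/ln 1.61 = 1.4, which is how index points would be compressed.

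**The case against.** Several stronger readings are tempting, and the documents do not support them.

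- A reader might infer that every odds ratio in the paper is biased. The reporting sentence also covers the univariable models. If all of those are reported whatever their p-value, their intervals keep nominal coverage for the unadjusted odds ratio.
- A reader might infer that every retained predictor is exaggerated. With uncorrelated predictors, inflation is negligible from an OR of about 2 at 10% incidence and about 1.5 at 50%.
- A reader might quote one coverage figure. The documents give no effect sizes, prevalences or correlations, and the candidate count differs by time point, so only a range is defensible.
- A reader might infer that the bootstrap is inadequate. It is unspecified rather than shown to be inadequate: if it repeated the selection it could supply a shrinkage factor. Even so, correcting optimism in performance does not restore interval coverage.
- A reader might infer that risks attached to the index are read off inflated odds ratios. Step 5 of *Development of the risk index* uses the observed CPSP proportion at each index value, and inflation common to all items cancels in relative points. Only uneven inflation distorts the score.

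It is also fair to say that this is mainly a prediction study, with a prediction-based sample size and a commitment to TRIPOD. Odds ratios are not its only product. But the aim names risk factors and the analysis section promises odds ratios with intervals.

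**Conclusion.** The point holds for the screened and eliminated multivariable models, and only for those. Direction is secure, because it follows from selecting and estimating in the same data with no stated adjustment. Magnitude is not secure: about 79 to 93% coverage instead of 95%, and a mean inflation of retained true log odds ratios of roughly 5 to 60%, depending on the assumptions listed in the tables. The low end of coverage needs correlated predictors with many weak effects, which is plausible for anxiety, depression, catastrophizing and the pain items but is not established by the documents. This should be changed before analysis. It does not threaten the feasibility of the study.

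**What to change.** In *Statistical analysis of results*, state that at each time point adjusted odds ratios and 95% intervals for all prespecified candidates, from the full multivariable model before any elimination, are the risk-factor evidence. Present the reduced model for prediction only. Shrink its coefficients using a bootstrap that repeats both the screen and the elimination in each resample, and do not label its model-based intervals as 95% confidence intervals. Because multiple imputation is planned, say how it is combined with the resampling.

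The cost is SAP wording, an extra table per time point and more computing; no new data are needed. Intervals will be wider and fewer factors will appear significant.

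The full model has its own limit. At 10% incidence, 1,500 patients give about 150 events: 150/37 ≈ 4 per parameter for the pooled list and 150/15 = 10 for the preoperative list. Full-model log odds ratios were still inflated by about 0 to 10% in the 27-candidate simulations, although coverage was close to nominal. The plan calls 1,500 sufficient ("a sample size of, at least, 1500 individuals is therefore sufficient to meet the main objective of the study"), but its own calculation scales to 15 × 1,500/1,799 = 12.5 parameters at 10% incidence and 15 × 1,500/1,124 = 20 at 50%. If incidence proves to be near 10%, keep the candidate list to about 12 parameters, chosen without looking at the outcome associations, or use a penalised fit, whose intervals need the same care in labelling.

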The treatments will be performed according to the rules and ethical standards on human experimentation and the Helsinki Declaration of 1964 (further revised in 2013). All study participants will provide written informed consent (including all the information about possible risks and side effects) for participation in the study. Every precaution will be taken to protect patient privacy.

For the development and validation of the prognostic models, the guidelines on prognostic modeling studies of individual participant data and the recommendations of the Transparent Reporting of a multivariable predict model for Individual Prognosis or Diagnosis (TRIPOD) will be followed.

➢ Population
 Inclusion criteria:
 Age ≥18 years
 Patients scheduled for elective surgery
 Exclusion criteria:
 Patients with perceptive (or sensorial) alterations of pain

Patients unable to communicate

Cognitive impairment

Insufficient knowledge of the Italian language.

Data collection

Recruitment is competitive. Each participating Center undertakes to include at least 20 patients in the study. Patients will participate in the study voluntarily and will not receive compensation of any kind from anyone, either directly or indirectly. Competitive enrollment means that being a multicentric research project, the number of patients included by each participating Center may vary depending on the inclusion capacity of each. There is therefore no maximum limit to the number of patients that each Center can include. The inclusion of patients in the study will end as soon as the total number of subjects described by the protocol is reached.

Web-based electronic case report forms (CRFs) will be used to collect data. All data will be anonymous and only the local principal investigator could match patients and reference numbers.

A comprehensive item pool was derived from a systematic literature search.

Data collection will record parameters at four different times:

- preoperative evaluation
- evaluation of the perioperative period (before surgery)
- evaluation of the perioperative period (after surgery)

• postoperative period

As regards the post-operative follow-up (three months after surgery), a telephone or outpatient evaluation is foreseen at the discretion of each center.

Preoperative evaluation (60 to 1 day before the scheduled procedur	e)
• Age	
18-35	
36-55	
≥55	
• Sex	
Female	
Male	
• BMI	
≤18.5 - 24.9	
25 - 29.9	
≥30	

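### The only planned validation is a bootstrap for optimism, which cannot show whether predicted risks stay calibrated in a centre not used to build the index; the data would allow that check.

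*Combined protocol and SAP*

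**What the plan says.** The Statistical analysis section names a single validation procedure: "Internal validation will be conducted using bootstrapping to correct for optimism". Performance is assessed for each model as a whole: "the discriminated ability will be evaluated via the C-statistic of the area under the ROC curve and calibration via the Hosmer-Lemeshow test". Neither that section, nor Development of the risk index, nor Power analysis mentions a centre effect, performance by centre, or a held-out centre.

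Methods refers to general guidance: "For the development and validation of the prognostic models, the guidelines on prognostic modeling studies of individual participant data", together with TRIPOD. It prescribes no procedure.

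The intended use goes beyond the study sample. Background aims at a valid risk index. Development of the risk index adds a cut-off for high risk and the proportion with CPSP at each index value. Power analysis asks for an equation that is "reliable when applied to new individuals in the target population".

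On centres:
- Expected number: "Authors estimate that, at least, 10 centers are needed to enroll the study population".
- Minimum size: "Each participating Center undertakes to include at least 20 patients in the study".
- Maximum size: "There is therefore no maximum limit to the number of patients that each Center can include".
- Follow-up at three months is by telephone or outpatient visit, as each centre decides (Data collection).
- The centre number is part of the eCRF code (Confidentiality).

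**The concern.** A bootstrap of patients redraws from the same hospitals in roughly the same proportions. It measures how much the model has adapted to chance features of that sample. It cannot show how far the baseline risk in another hospital lies from the pooled baseline.

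This matters because the output is an absolute risk per score and a cut-off. Both move when baseline risk moves, even if patients are still ranked equally well. Two features of the design could produce such shifts: centre-specific mode of outcome assessment, and centre sizes ranging from 20 to no limit, which allow a few centres to set the pooled baseline. Without a check by centre, the report could not tell a future user whether the tabulated risks apply locally or need recalibration first.

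**Working it through.** **1. The plan's own figures.** The stated sizes follow from the shrinkage criterion of the cited sample-size method, n = P / [(S − 1) ln(1 − R²/S)]. Here S = 0.9 (assumed; not stated), and R² is 15% of the maximum Cox-Snell value.
- 50% incidence, P = 15: maximum 0.75, R² = 0.1125; n = 15 / (0.1 × 0.1335) = 1123.3, so 1124.
- 10% incidence: maximum 0.478, R² = 0.072 after rounding; n = 15 / (0.1 × 0.08338) = 1799. With P = 12, n = 1440.

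All three reproduce. The criterion limits overfitting and has no term for centres, so meeting it does not address the point.

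**2. Why the bootstrap is blind here.** A logistic model with an intercept has mean predicted risk equal to mean observed risk in its own data. Resampling patients from the pooled data therefore gives calibration-in-the-large near zero, however much centres differ.

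**3. Size of the true error, under assumption.** The documents give no between-centre figure. Let residual centre effects be normal with SD τ on the logit scale. The share of centres off by more than 0.5 logits is 2 × [1 − Φ(0.5/τ)]:
- τ = 0.3: 0.5/0.3 = 1.67, giving 9.6%.
- τ = 0.5: 0.5/0.5 = 1.00, giving 31.7%.

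Around an assumed 20% incidence (logit −1.386), a shift of ±0.5 logits means a true risk of about 13% or 29%.

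**4. What a held-out analysis would show.** Two illustrative simulations were run; all settings are assumptions.

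(a) Calibration-in-the-large: 12 binary predictors, 20% incidence, 1500 patients, 60 datasets per setting. The table gives the share of held-out centres with observed error above 0.5 logits.

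| Between-centre SD | 10 centres of 150 | 12 unequal centres, those with at least 40 patients held out |
|---|---|---|
| 0 | 4% | 9% |
| 0.3 | 24% | 23% |
| 0.5 | 35% | 43% |

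In the unequal-centre runs, bootstrap calibration error was about 0.01 logits at every SD. The held-out figures exceed those in step 3 largely because of sampling noise. The standard error of calibration-in-the-large is roughly 1/√[np(1 − p)]: 1/√(40 × 0.2 × 0.8) = 0.40 for 40 patients, and 1/√(150 × 0.2 × 0.8) = 0.20 for 150. The non-zero first row is noise too.

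(b) Discrimination and observed/expected: 10 centres of 150, 12 binary predictors, 60 datasets, no variable selection. Centre variation was either none or SD 0.5 in the intercept and 0.3 in each coefficient.

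| Quantity | No variation | With variation |
|---|---|---|
| Bootstrap-corrected C | 0.681 | 0.680 |
| Mean C in new centres | 0.683 | 0.677 |
| SD of log(observed/expected), held-out centres | 0.15 | 0.39 |
| SD of log(observed/expected), new centres | 0.09 | 0.34 |

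The loss is in calibration, not average discrimination. Leaving out centres shows it; the bootstrap C does not.

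**5. Feasibility.** With 10 equal centres (assumed), each turn holds out 1500/10 = 150 patients, of whom 15 have events at 10% incidence or 75 at 50%, and refits on 1350.
- Single block: the 95% half-width for C (Hanley-McNeil, C of 0.70 to 0.75) is about 0.15 at 10% incidence and 0.08 at 50%.
- Pooled over 10 blocks, with between-centre SD of C from 0 to 0.05: about 0.05 to 0.06 at 10%, and 0.025 to 0.04 at 50%.
- A centre of 20 patients has 2 to 10 events and a half-width of about 0.22 to 0.43, so such centres must be grouped.
- Expected shrinkage with 12 parameters at 10% incidence falls only from 0.903 (n = 1500) to 0.894 (n = 1350).

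**The case against.** The plan correctly calls its bootstrap internal and claims no tested transportability. The phrase about new individuals introduces the sample-size argument and is not a statement about centres. Testing in other hospitals is often left to a later study. This stands: nothing in the plan is false, and the point is a missed check measured against the study's own aim.

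A reader might take the 10% to 50% incidence range as evidence that centres differ widely. The documents give that range by type of surgery. Site and technique of surgery are collected as candidate predictors, so the model can absorb part of it.

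A reader might also infer that risks in a new hospital would commonly be wrong by a factor of two. From 20%, doubling needs 0.98 logits and halving 0.81. At SD 0.5 about 8% of centres would pass one of those limits (upper tail at 0.98/0.5 = 1.96, lower at 0.81/0.5 = 1.62); at SD 0.3, about 0.4%. Nor would the study report near-perfect optimism-corrected calibration, since its only planned calibration measure is the Hosmer-Lemeshow test.

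The remedy has limits as well. A block of 100 patients at 10% incidence has about 10 events and a standard error near 1/√(100 × 0.1 × 0.9) = 0.33 logits. Grouping centres averages away some of the variation sought, and about ten blocks give an imprecise prediction interval. These limits affect how results are read; they do not make the bootstrap informative about centres.

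**Conclusion.** The gap is real and worth closing, as an inexpensive improvement and not as the correction of an invalid analysis. As written, the plan can support internal validity of the index but cannot show that its absolute risks and cut-off hold in a centre outside the development data. General references to TRIPOD and to "the guidelines on prognostic modeling studies of individual participant data" leave room for such a check but prespecify none.

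The size is conditional. For an assumed residual SD of 0.3 to 0.5 logits, about 10% to 32% of centres would have a true calibration-in-the-large error above 0.5 logits, unseen by the pooled bootstrap. The documents contain nothing from which to estimate that SD, and it could be smaller. That a few large centres will dominate is permitted by the recruitment rules but not known.

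**What to change.** Keep the bootstrap, and keep the final model on all patients. Add to the Statistical analysis section:

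- Internal-external cross-validation that repeats the whole model-building process, including imputation, backward elimination and score assignment, leaving out one centre at a time. Small centres are grouped by a rule fixed in advance, so that each held-out block has enough events.
- For each block: C, calibration-in-the-large (or observed/expected) and calibration slope, with confidence intervals; then a random-effects summary with a prediction interval. State that single-block estimates will be imprecise if incidence is near 10%, and that grouping can hide some variation.
- A rule for the conclusion: if calibration varies materially between blocks, report that the index needs local intercept recalibration before use. If the check is not done, or is too imprecise to inform, limit the conclusion to internal validity.

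The cost is SAP wording and analysis time; the centre number is already recorded and no further patients are needed. The downsides are imprecise block estimates and possibly less favourable reported performance. The rule should be fixed before the data are examined, because by-centre results chosen afterwards would carry less weight.
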